### **9.6.2 Lung Clearance Index**

The LCI will be assessed in CF patients with baseline ppFEV1 >70% in Cohorts 2b- 4b and for all subjects in Cohort 6. In CF Cohorts 2b-4b, three acceptable LCI values at each study visit are planned to be collected. In Cohort 6, two acceptable LCI values at each study visit are expected. At each visit, the average value of acceptable LCI measurements will be used. If only one acceptable value is collected, then the single acceptable value will be used. Additionally, use of an inhaled bronchodilator will be recorded at each LCI assessment. All LCI summaries will identify use of an inhaled bronchodilator as recorded on the LCI eCRF.

Descriptive statistics summaries of LCI will be provided by scheduled visit. Absolute changes from baseline will be included. In addition to an overall summary, subgroup analyses (as defined in Section 4.2) will be provided.

A sensitivity analysis of LCI will be performed if use of an inhaled bronchodilator at any post-baseline assessment does not match use of an inhaled bronchodilator at the baseline assessment for any CF patients. The sensitivity analysis will consist of a summary of LCI values with absolute changes from baseline by scheduled visit, excluding any post-baseline LCI assessments where the bronchodilator status does not match the bronchodilator status at baseline. Subgroup analyses will not be provided for the sensitivity analysis.

Plots of mean (+/- SD) LCI over time will be provided by study day from baseline to the EOS visit. Plots will additionally include a plot from baseline to Day 37 (Cohorts 2b-4b) and a plot from baseline to Day 43 (Cohort 6).

All LCI data will be listed by subject.

### 9.6.3 Revised Cystic Fibrosis Questionnaire

The CFQ-R will be collected at scheduled timepoints for CF patients only. The questionnaire provides information about demographics, quality of life, and daily activities.

CFQ-R has a total of 50 questions to form 12 domains. Question 43, which is scored 1, 2, 3, 4, or 5, is not used in calculating any domain; all the other 49 questions are scored 1, 2, 3, or 4.

To calculate the score for each domain, the response scores on the negatively phrased questions are reversed (reversed scores = 5 – response scores) so that 1 always represents the worst condition and 4 always represents the best condition.

The scaled score for each domain ranges from 0 (worst condition) to 100 (best condition) and will be calculated as follows:

$$\text{Scaled score for a domain} = 100 \times [\text{mean}(\text{scores of all questions in that domain}) - 1] / 3$$

The scaled score for a specific domain will not be calculated if more than half of the questions in the domain have missing scores.

The table below provides the questions included in each domain, the questions with the reversed scores, as well as the maximum number of missing questions for a domain score to be calculated.

CFQ-R for Adolescents and Adults

Domain	Questions		Reversed Questions	Max # of missing Questions
	Total	Individual		
Physical	8	1, 2, 3, 4, 5, 13, 19, 20	13	4
Role	4	35, 36, 37, 38	35	2
Vitality	4	6, 9, 10, 11	6,10	2
Emotion	5	7, 8, 12, 31, 33	-	2
Social	6	22, 23, 27, 28, 29, 30	23,28,30	3
Body	3	24, 25, 26	-	1
Eat	3	14, 21, 50	-	1
Treatment Burden	3	15, 16, 17	15,17	1
Health perceptions	3	18, 32, 34	18,32,34	1
Weight	1	39	-	0
Respiration*	6	40, 41, 42, 44, 45, 46	43	3
Digestion	3	47, 48, 49	-	1

\*Question 43 not used to calculate a domain

---

A descriptive statistics summary of CFQ-R domain scores and absolute changes from baseline by scheduled timepoint will be provided.

All CFQ-R data will be listed by subject.

#### **9.6.4      Rate of Pulmonary Exacerbations**

Pulmonary exacerbation assessments will be collected at scheduled timepoints for CF patients. CF-related exacerbation rates are important clinical events associated with disease progression, and they remain a significant issue even in patients receiving CFTR modulator therapy (Middleton 2019).

A descriptive statistics summary displaying the number and percent of subjects reporting pulmonary exacerbation assessments (Y/N), as well as the total number of exacerbations reported will be provided by scheduled visit.

All pulmonary exacerbation assessment data will be listed by subject.

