maximum observed plasma concentration (C_{\max}), area under the plasma concentration time curve (AUC) from time 0 to 24 hours (AUC_{0-24}), AUC from time 0 to the last quantifiable plasma concentration (AUC_{last}), AUC from time 0 extrapolated to infinity (AUC_{inf}), and terminal elimination half-life ($t_{1/2}$). Additional PK parameters may be calculated as needed. Pharmacokinetic parameters will be determined using non-compartmental methods. Descriptive statistics of PK parameters will include mean, standard deviation (SD), coefficient of variation, median, minimum, and maximum. PK results will be analyzed for dose proportionality, and sex differences.

PK population: All NHVs and CF patients that received at least one dose of study drug and that have measurable PK concentration data. A subject may be excluded from PK summary and statistical analysis if the subject has a protocol deviation(s) that is thought to impact PK analysis.

NHV Pharmacodynamic (PD) Effect Assessment:

Results, including percent change and duration of response from baseline to EOS will be analyzed and summarized by cohort. The NHV PD population includes subjects in NHV cohort 5.

CF Patient Efficacy Assessments:

Descriptive summary of ppFEV1, LCI, BMI and CFQ-R respiratory domain score at each scheduled study visit and change from baseline will be summarized. Events rate of pulmonary exacerbation will be summarized by cohort.

Immunogenicity (Anti-Drug Antibodies):

Shift tables will be displayed by cohort or by dose in both healthy volunteers and CF patients.

Baseline for data analysis purposes is defined as the pre-dose value occurring closest to the first dose of ARO-ENaC or PBO administered in the study.

Additional details will be provided in the statistical analysis plan.

Table 1.1: Cohorts 1-4:

Assessment	Screen	Day -1 Confine	R	Day 1	Day 2	Day 3	Day 4	Day 5	Day 8	Day 15	Day 29 EOS	Early Term.
Visit Windows	Days -28 to -1			± 5 min for 30 min post dose PK draw and ± 10 min for all other post dose PK timepoints only					± 2 d			
Informed Consent	X											
Eligibility Criteria	X	X										
Body Mass Index/Weight/Height	X			X					X	X	X	X
Demographics	X											
Medical History	X	X										
Drug Screen	X											
Hepatitis/HIV Serology Screen	X											
Physical Exam (may be symptom directed after Day 1)	X			X (pre-dose)	X	X	X	X	X	X	X	X
FSH (in women of post-menopausal age only)	X											
Urine qualitative pregnancy test	X			X (pre-dose)							X	X

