6.3. Exploratory Endpoints

1. Changes from pre-dose baseline in FEV1 in CF patients
2. Changes from pre-dose baseline in lung clearance index (LCI) in CF patients
3. Changes from pre-dose baseline in the revised cystic fibrosis questionnaire (CFQ-R) in CF patients
4. Rate of pulmonary exacerbations in CF patients receiving ARO-ENaC versus PBO
5. Changes from pre-dose baseline in body mass index (BMI) in CF patients
6. Plasma metabolite identification in NHVs (reported in a separate report outside of this study)
7. Determination of urinary excretion and metabolite identification in NHVs (reported in a separate report outside of this study)
8. Changes from pre-dose baseline to Day 18 in expression of ENaC using bronchoscopic brush biopsy samples in NHVs
9. Changes from pre-dose baseline to Day 18 in expression of ENaC using bronchoalveolar lavage (BAL) samples in NHVs
10. Changes from pre-dose baseline to Day 18 in cytokine levels as well as cell count and differential in BAL fluid in NHVs

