7.6. Duration of the Study

For each NHV subject the approximate duration of the study clinic visits is a maximum of 8 weeks from the beginning of the Screening period to the Day 29 End-of-Study (EOS) examination.

For each CF patient, the duration of the study is approximately 20 weeks from the beginning of the Screening period to the Day 113 EOS examination.

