### **7.3 Primary Analysis**

Primary analysis will occur when all subjects in Cohort 6 have completed their Day 43 visit (or have discontinued early) and all other cohorts have completed. EMB and the Sponsor may be unblinded after the data have been entered and cleaned.

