## **9. STATISTICAL METHODS OF ANALYSIS**

For all summary tables and figures described in this SAP, NHV Cohorts 1-5 and CF patient Cohorts 2b-4b and 6 will be summarized separately. Subjects will be grouped by dose and dosing regimen within each table and figure, with subjects receiving placebo pooled across cohorts. All data will be combined in listings, which will be sorted by cohort and subject number.

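### SAP 9.6.4 does not produce the exacerbation rate that the endpoint names, and at the primary analysis cumulative summaries against pooled placebo rest on unequal follow-up

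*SAP*

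**What the plan says.** Protocol section 6.3 lists as an exploratory endpoint "Rate of pulmonary exacerbations in CF patients receiving ARO-ENaC versus PBO", and SAP 2.1 repeats it. The CF efficacy paragraph of the protocol synopsis adds: "Events rate of pulmonary exacerbation will be summarized by cohort". Protocol 12.6 names the rate of CF exacerbations among the measures to be described by scheduled visit.

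SAP 9.6.4 carries the word rate in its title. What it specifies is the number and percent of subjects by a yes/no assessment, "as well as the total number of exacerbations reported will be provided by scheduled visit". No denominator in time at risk appears there or elsewhere in the SAP. SAP section 10 reports no major difference from the protocol's analyses.

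Three other provisions bear on how such a table would read:

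- SAP section 9 groups subjects by dose and regimen, "with subjects receiving placebo pooled across cohorts".
- SAP 7.3 times the primary analysis for when "all subjects in Cohort 6 have completed their Day 43 visit (or have discontinued early) and all other cohorts have completed".
- Protocol 7.6 runs each CF patient "from the beginning of the Screening period to the Day 113 EOS examination".

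Neither document states a common data cut for the primary analysis. SAP 2.2 rules out formal testing. Protocol 7.5 and SAP 7.4 provide for a final analysis on the complete data.

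**The concern.** A rate needs events and time at risk. Counts and percentages can stand in for it only when groups are followed for the same time, and at the primary analysis they are not. All 18 active subjects in Cohort 6 may be part-way through follow-up, while 7 of the 13 pooled placebo subjects have finished. A reader who adds up the visit rows, or reads an overall percentage, would compare groups with different time to have an event.

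At stake is an early impression of the newest regimen on an outcome that SAP 9.6.4 itself calls clinically important, taken from a table that cannot separate a drug effect from shorter observation. Apart from timing, the named endpoint is not estimated at any analysis.

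**Working it through.** The documents give no exacerbation rate, event count or power statement for this endpoint, so there is no planned figure to reproduce.

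**Inputs.** Planned numbers (Protocol Table 4; SAP 3.1): Cohort 6 has 18 active and 6 placebo; Cohorts 2b, 3b and 4b have 2 + 2 + 3 = 7 placebo; pooled placebo is 13. Full CF follow-up is 113 days. The Cohort 6 minimum at the primary analysis is 43 days. *Assumed, because the documents are silent:* uniform Cohort 6 accrual over A days, no withdrawals, and equal true event rates in all groups.

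**1. Mean Cohort 6 follow-up, F.** A subject enrolled t days before the last one has min(43 + t, 113) days.
- For A up to 70: F = 43 + A/2.
- For A above 70: F = 113 − 70²/(2A) = 113 − 2450/A.

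**2. Pooled placebo.** Person-days = 7×113 + 6F = 791 + 6F; the mean is that divided by 13. Cohort 6 active person-days = 18F.

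**3. Results with no drug effect.**

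| A (days) | F | Placebo mean | Placebo mean / F | Expected per-subject events, Cohort 6 active / placebo | Expected raw total, Cohort 6 active / placebo |
|---|---|---|---|---|---|
| 0 (bound) | 43 | 1049/13 = 80.7 | 1.88 | 0.53 | 774/1049 = 0.74 |
| 30 | 58 | 1139/13 = 87.6 | 1.51 | 0.66 | 1044/1139 = 0.92 |
| 60 | 73 | 1229/13 = 94.5 | 1.30 | 0.77 | 1314/1229 = 1.07 |
| 90 | 85.8 | 100.4 | 1.17 | 0.85 | 1.18 |
| 180 | 99.4 | 106.7 | 1.07 | 0.93 | 1.29 |
| Final analysis | 113 | 113 | 1.00 | 1.00 | 2034/1469 = 1.38 |

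**4. Where raw totals change direction.** 18F = 791 + 6F gives F = 791/12 = 65.9 days. Below that, totals favour Cohort 6; above it, its larger group (18 v 13) makes them count against it.

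**5. Percent with at least one event, at the bound F = 43.** For an assumed Poisson rate r per year, the probability over t days is 1 − exp(−r·t/365.25). At r = 1 this is 11.1% over 43 days and 26.6% over 113 days, so pooled placebo is (7×26.6 + 6×11.1)/13, which is 19.5% before rounding of the inputs. At r = 0.5 the comparison is 5.7% v 10.4%; at r = 2 it is 21.0% v 34.5%. Expected totals at r = 1 are 774/365.25 = 2.1 events on Cohort 6 active and 1049/365.25 = 2.9 on placebo.

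**6. With a time denominator.** Events per person-time have an expected ratio of 1.00 at any F if the rate is constant over follow-up. Cutting every CF subject at Day 43 also equalises per-subject follow-up (774/18 = 559/13 = 43 days).

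**7. Visit rows.** The schedules in Protocol Tables 1.3 and 1.4 differ: Day 37 then Day 57 in Cohorts 2b–4b, but Days 36, 43 and 57 in Cohort 6. If events are booked to the visit at which they are reported, the shared Day 57 row covers 20 days in Cohorts 2b–4b and 14 in Cohort 6. Pooled placebo then averages (7×20 + 6×14)/13 = 17.2 days against 14. This uses the visit-day headings. The exacerbation row of Table 1.3 is not fully legible in the text available, so the exact assessment intervals in 2b–4b are not confirmed.

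**The case against.** The strongest reply is that this is a descriptive, exploratory endpoint shown visit by visit, as Protocol 12.6 asks. Percentages are given as well as counts. Shorter follow-up in Cohort 6 mainly thins the late rows (Day 57 onward) and does not distort each row; the problem appears when rows are summed. The table shells sit in a companion document and may add a rate. Cohort 6 active and its own 6 placebo subjects have the same planned follow-up, and the final analysis brings every CF cohort to a planned 113 days. With two or three events expected per group at one event per year, a rate would carry a very wide interval.

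Most of that stands, and it limits the point. It does not supply the missing rate. The shells cannot be relied on for a quantity that the SAP text never defines. The by-visit layout is not a full remedy either, because the visit days differ. Even at the final analysis, withdrawals, and replacements under Protocol 8.4, leave actual time at risk unequal in the all-dosed set.

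A reader might also infer that raw event totals favour Cohort 6. The documents do not support that. It holds only if mean Cohort 6 follow-up is below about 66 days; no accrual period is given, and in three of the four accrual periods shown the totals run the other way.

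**Conclusion.** The point holds in a limited form. The protocol and SAP name a rate; the SAP's method yields none, at the primary or the final analysis, and declares no change.

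At the primary analysis, cumulative per-subject counts and percentages against pooled placebo tilt toward Cohort 6 whenever its mean follow-up is below 113 days. The follow-up imbalance is 1.07- to 1.51-fold for assumed uniform accrual over 180 down to 30 days. The 1.88-fold figure is an upper bound that needs every Cohort 6 subject to be exactly at Day 43, and should not be read as the expected size. These figures assume planned numbers, no withdrawals and no drug effect; the percentages also assume a Poisson event rate that the documents do not give.

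It would be too strong to say that the randomised comparison within Cohort 6 is biased, or that the cut-off imbalance carries into the final analysis: planned follow-up is equal in both cases. Severity is low.

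**What to change.** In SAP 9.6.4, add exacerbations per person-year by treatment group, computed as events divided by total time from first dose to EOS, withdrawal or data cut, with an exact Poisson 95% interval. Label it as descriptive estimation, which is consistent with SAP 2.2. For the primary analysis, state the data cut used, and show Cohort 6 active beside its 6 concurrent placebo subjects as well as beside pooled placebo. Keep the by-visit counts and percentages as support.

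The cost is a few sentences in the SAP and a small amount of programming on dosing, visit and withdrawal dates that the study already needs. The intervals will be wide because few events are expected, and they will be too narrow if events cluster within patients; both should be said in the table note. An event rate also needs a rule for when a repeat episode counts as new. Protocol 16.1 gives none, and the planned event total already depends on one.

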#### **9.6.5      Body Mass Index**

Height and weight measurements will be collected at scheduled timepoints per the Protocol, and BMI will be derived. BMI measurements will be included in vital signs reporting, described in Section 9.5.3.

#### **9.6.6      $\alpha$ ENaC mRNA Expression**

Only NHVs from Cohort 5 will undergo bronchoscopies to evaluate  $\alpha$ ENaC mRNA knockdown. Bronchoscopies will be performed at baseline and on Day 18.

A descriptive statistics summary of  $\alpha$ ENaC mRNA expression will be provided by scheduled visit. Derived changes from baseline will be included.

All bronchoscopy data will be listed by subject.

### **9.7          Pharmacokinetic Analyses**

All PK summaries outlined in this section will be created using the PK Analysis Set. PK summaries will additionally include the geometric mean and the geometric coefficient of variation (CV). The geometric CV will be calculated as:

$$\text{geometric CV} = \text{sqrt}(\text{e}^{[(\text{SD of log-transformed data})^2]} - 1) * 100\%$$

The Sponsor will provide NCA of PK data (Appendix B).

#### **9.7.1        Plasma Concentrations**

Descriptive statistics summaries of plasma concentrations will be provided by scheduled timepoint. Concentrations below the limit of quantification (BLQ) will be set to zero for summary statistics.

Mean plasma concentrations (+SD) will be plotted on a linear and semi-logarithmic scale versus nominal time points by treatment. Individual plasma concentrations will be plotted on a linear and semi-logarithmic scale versus actual sampling times. For each cohort, spaghetti plots of individual plasma concentrations on a linear and semi-logarithmic scale will also be presented. A reference line indicating the lower limit of quantification (LLOQ) will be included in plots, as appropriate.

Actual sampling times that are outside the sampling window ( $> \pm 10\%$  of nominal time) will be listed, but will be excluded from descriptive statistic summaries of concentration data.

All plasma concentration data will be listed by subject.

### 9.7.2 Urine Amounts Excreted

Descriptive statistics summaries of urine amounts excreted will be provided by scheduled collection interval.

All urine amounts excreted will be listed by subject.

### 9.7.3 Pharmacokinetic Parameters

Plasma PK parameters will be calculated for Day 1, Day 3, and Day 1\_3. Urine PK parameters will be calculated for Day 3 only.

Parameter	Definition
Plasma PK Parameters	
Cmax	Maximum observed concentration
Tmax	Time to reach maximum plasma concentration
AUC0-24	The area under the plasma concentration versus time curve from the zero to 24 hours
AUClast	The area under the plasma concentration versus time curve from the zero to the time of last quantifiable plasma concentration
AUCinf	The area under the plasma concentration versus time curve from zero to infinity
t 1/2	Apparent terminal elimination halflife
RACmax	Apparent drug accumulation calculated by Cmax of last dose vs first dose
RAAUC	Apparent drug accumulation calculated by AUC of last dose vs first dose
Urine PK Parameters	
Ae0_24	Amount recovered in urine over 0 - 24 hours post dose (Day 3 only)
Fe0_24	Percentage of the administrated drug recovered in urine over 0 - 24 hours (Day 3 only)

CLr

Renal clearance over a time interval calculated by  $A_e/AUC$  at the same time interval (0 - 24 hours, Day 3 only)

Additional PK parameters in each part may be determined where appropriate.

Plasma and urine PK parameters will be listed and summarized descriptively by treatment. Summary statistics of Tmax will not include geometric mean and geometric CV. Diagnostic PK parameters will be listed only.

#### 9.7.4 Dose Proportionality Analysis

The Cmax and AUCinf ARO-ENaC PK parameters from Day 1 and Day 1\_3 will be compared across each dose level (RDD) to assess dose proportionality. If AUCinf cannot be determined reliably for all subjects or treatments, an alternative AUC measure, such as AUC to a fixed timepoint or AUClast, may be used in the statistical analysis of dose proportionality. Analyses for NHV and CF patients will be performed separately. Statistical analyses will be done using a power model with the following general form:

$$\ln(\text{PK parameter}) = \alpha + \beta * \ln(\text{dose}) + \varepsilon$$

where  $\alpha$  is the y-intercept,  $\beta$  is the slope, and  $\varepsilon$  is the error. Estimates of  $\alpha$  and  $\beta$ , and 90% confidence intervals (CIs) for  $\beta$ , will be provided for each PK parameter. Dose proportionality will be indicated if the Cmax and AUC 90% CIs for  $\beta$  all contain 1. The SAS code will be similar to the following:

```
proc reg data=adpp;
  by parameter;
  model ln(aval) = ln(dose) / clb alpha=0.1;
run;
```

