Table 1.3: CF patient multi-dose cohorts (Cohorts 2b, 3b, 4b)

Assessment	Screen	R	Day 1	Day 2	Day 3	Day 15	Day 22	Day 23	Day 24	Day 29	Day 37	Day 57	Day 71	Day 85	Day 113 (EOS) or Early Term.
Visit Windows	Days -28 to -1					± 2d		± 5 min for 30 min post dose PK draw and ±10 min for all other post dose PK timepoints only		± 2d	± 5d				
Informed Consent	X														
Eligibility Criteria	X														
Body Mass Index/Weight/Height	X														
Demographics	X														
Medical History	X														
Drug Screen	X														
Hepatitis/HIV Serology Screen	X														
Physical Exam (may be symptom directed after Day 1)	X														
FSH (in women of post-menopausal age only)	X														
Urine qualitative pregnancy test (pre-dose to begin each cycle)	X														X
ECG ¹	X														
Vital Signs (BP, temp, pulse ox., RR, heart rate) perform before other evaluations	X														
Clinical Labs (heme, coag, chem, UA, Urine electrolytes) Completed pre-dose on dosing days ⁴	X														
Chest X-ray (PA and Lateral) ⁵															X
PK ²															
Lung Clearance Index ⁶															
CF Genotyping (See protocol for specifications)	X														
CF Questionnaire															
Spirometry	X														
Concomitant Meds/Therapies	X														
Adverse Events	X														

Dose Administration (PBO or Active) ⁷			X	X	X		X	X	X						
Urine Cotinine	X														
Anti-drug antibodies		X				X									X
Evaluate and Record Occurrence of Pulmonary Exacerbation						X					X	X	X	X	X
Sweat Chloride ⁸			X (pre-dose)												

1. ECG completed pre-dose (-4hrs ± 30 min) and 2 hours (± 30 min) post-dose on dosing days; any abnormal ECGs will be repeated in triplicate with each measurement approximately 1 minute apart.
2. Plasma PK collected Cycle 1:
 - a. Day 1: pre-dose, then based on start of inhalation 30, 60, 120 min, 4 hour
 - b. Day 2: pre-dose (Day 1, 24 hour time point), then based on start of inhalation 60 min, 120 min, 4hour.
 - c. Day 3: pre-dose (Day 2, 24 hour time point), then based on start of inhalation, 30, 60, 120 min, 4 hour
3. Spirometry completed pre-dose and post-dose 60 min (± 20 min), 120 min (± 20 min) on dosing days. Spirometry is only completed once on days when dose is not administered.

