6.2. Secondary Endpoints

1. Changes from pre-dose baseline in serum electrolytes in NHVs and CF patients as a safety measure.
2. Changes from pre-dose baseline in Forced Expiratory Volume (FEV1) in NHVs as a measure of safety.

3. Pharmacokinetics of ARO-ENaC in NHVs and in CF patients

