## 2.2 Hypotheses and/or Estimations

No formal hypothesis testing will be performed.

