#### **14.1.2.1 Criteria for the Calculation of Apparent Terminal Elimination Rate Constant and Half-life**

The start of the terminal elimination phase for each subject will be defined by visual inspection and generally will be the first point at which there is no systematic deviation from the log-linear decline in concentrations.

The apparent terminal elimination rate constant ( $\lambda_z$ ) will only be calculated when a reliable estimate can be obtained using at least 3 data points, not including Cmax, and the adjusted coefficient for determination of exponential fit (R2-adj) of the regression line is  $\geq 0.7$ . Parameters requiring  $\lambda_z$  for their calculation (eg, AUCinf, t1/2, CL, and Vz) will only be calculated if the R2-adj value of the regression line is  $\geq 0.7$ .

The following regression-related diagnostic PK parameters will be determined, when possible.

Parameter	Units	Definition
$\lambda_z$	1/h	apparent terminal elimination rate constant
$\lambda_z$ N	NA	number of data points included in the log-linear regression
$\lambda_z$ Span Ratio	NA	time period over which $\lambda_z$ was determined as a ratio of t1/2
R2-adj	NA	adjusted coefficient for determination of exponential fit

Where possible, the span of time used in the determination of  $\lambda_z$  (ie, the difference between  $\lambda_z$  Upper and  $\lambda_z$  Lower) should be  $\geq 2$  half-lives. If the  $\lambda_z$  Span Ratio is  $< 2$ , the robustness of the t1/2 values will be discussed in the PK report.

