#### 14.1.2.2 Criteria for Calculation and Reporting of Area Under the Concentration-time Curve

The minimum requirement for the calculation of area under the concentration-time curve (AUC) will be the inclusion of at least 3 consecutive concentrations above the lower limit of quantification. If there are only 3 consecutive concentrations, at least 1 should follow Cmax.

If the extrapolated area is  $>20\%$ , AUCinf (and derived parameters) may be excluded from the summary statistics and statistical analysis at the discretion of Sponsor clinical pharmacology representative.

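### SAP 9.7.4 takes 90% CIs for the slope that contain 1 as showing dose proportionality, so imprecise data make that conclusion easier to reach

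*SAP*

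**What the plan says.** SAP 9.7.4 fits a power model, the log of the PK parameter on the log of respirable delivered dose (RDD), separately for healthy volunteers (NHV) and CF patients. It covers Cmax and AUCinf, for Day 1 and for Day 1_3. The slope and its 90% CI are reported for each parameter. A decision sentence follows: "Dose proportionality will be indicated if the Cmax and AUC 90% CIs for" the slope all contain 1.

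The section lets the AUC measure change: "If AUCinf cannot be determined reliably for all subjects or treatments, an alternative AUC measure" may be used. Appendix B restricts AUCinf further. The terminal rate constant "will only be calculated when a reliable estimate can be obtained using at least 3 data points, not including Cmax" (14.1.2.1), and an AUCinf with more than 20% extrapolated area "may be excluded from the summary statistics and statistical analysis at the discretion of Sponsor clinical pharmacology representative" (14.1.2.2).

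PK is a secondary endpoint (Protocol 6.2: "Pharmacokinetics of ARO-ENaC in NHVs and in CF patients"), and the Protocol Synopsis says "PK results will be analyzed for dose proportionality, and sex differences". SAP 2.2 states that "No formal hypothesis testing will be performed". The PK text in the Synopsis, Protocol 12.5, SAP 2.2 and SAP 9.7.4 give no acceptance range for the slope, no limit on interval width and no inconclusive category.

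**The concern.** A 90% CI that contains 1 says only that a slope of 1 was not rejected at the 10% level. It does not say that the slope is close to 1. A very wide interval contains 1 along with slopes that would mean severe non-proportionality, and the rule passes it.

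The incentive therefore runs the wrong way. If the true slope differs from 1, more variability or fewer evaluable subjects raises the chance of passing. If the true slope is exactly 1, each interval contains 1 in 90% of trials whatever the precision, so better data bring no reward.

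The word all is also unclear. It could mean Cmax and AUC within one day (two intervals) or both days together (four intervals), and these readings have different error rates.

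At stake is a statement in the study report, on a secondary endpoint, that proportionality is indicated when the data are merely imprecise.

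**Working it through.** The plan gives no power or error rate for this rule, so there is no stated figure to reproduce. The code option alpha=0.1 does match the 90% CI in the text.

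**Inputs from the documents.** RDDs are from Protocol 5.8, Table 3, and active numbers from the Synopsis.
- NHV: 2.9, 6.6, 12.5, 30.7 mg with n = 4, 4, 4, 12 (cohorts 4 and 5 combined); total 24.
- CF Day 1: 6.6, 12.5, 30.7, 92.1 mg with n = 4, 4, 9, 18; total 35.
- CF Day 1_3: the first three CF levels, n = 4, 4, 9; total 17. Cohort 6 is left out because it is dosed on Days 1, 15 and 29. The SAP does not define Day 1_3, so this is an inference.

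**Assumptions.** Full enrolment, full evaluability, maximum doses, and a CV of 30, 50, 80 or 100%.

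**Formulas.** Sxx = Σ nᵢ(ln dᵢ − weighted mean)²; σ = √ln(1+CV²); SE = σ/√Sxx; half-width = t(0.95, n−2) × SE. P(CI contains 1) is the probability that a noncentral t with n−2 df and noncentrality (β−1)/SE lies within ±t(0.95, n−2). With r the ratio of highest to lowest RDD, the departure from proportionality over the range is r^(β−1).

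**Worked case, NHV, CV 50%, β = 1.2.** The weighted mean of ln RDD is 2.625. Sxx = 9.74 + 2.18 + 0.04 + 7.66 = 19.62. σ = √ln 1.25 = 0.472. SE = 0.472/√19.62 = 0.107. Half-width = 1.717 × 0.1066 = 0.183. Noncentrality = 0.2/0.1066 = 1.88, which gives P = 0.431.

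**True slope 1.2, all three fits** (percentages are for CV 30/50/80/100%):

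| | NHV | CF Day 1 | CF Day 1_3 |
|---|---|---|---|
| r | 10.59 | 13.95 | 4.65 |
| Sxx | 19.62 | 31.53 | 7.10 |
| Departure r^0.2 | 1.60-fold | 1.69-fold | 1.36-fold |
| Two CIs contain 1, % | 3–6 / 26–33 / 51–57 / 58–64 | <1 / 11–16 / 36–43 / 46–52 | 29–36 / 56–62 / 70–74 / 73–77 |
| One CI contains 1, % | 10 / 43 / 66 / 73 | 2 / 25 / 53 / 63 | 46 / 71 / 81 / 84 |

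The two-CI row is Cmax and AUC for one day, from 40,000 simulated trials, with the range covering assumed correlations of 0.5 to 0.8. If all means four CIs, the rates are 1–3/14–25/35–48/43–55% (NHV) and <1/8–14/28–36/36–45% (CF). On every reading the rate rises with noise.

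**What a single interval can pass at CV 50%.** The largest passing estimate is 1 + half-width: 1.18 (NHV), 1.14 (CF Day 1) and 1.31 (CF Day 1_3). The upper limit at that estimate is 1 + 2 × half-width, a departure of r^(2 × half-width) = 2.37-, 2.12- and 2.60-fold. Even an estimate of exactly 1 has a 90% CI for r^(β−1) of 0.65–1.54, 0.69–1.46 and 0.62–1.61.

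**A truly proportional drug** fails in 10% of trials on one CI and 10–19% on two. On four it fails in about 10–34% (NHV) or 18–34% (CF), depending on correlation; the upper end is 1 − 0.9⁴ = 0.344.

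**Fewer evaluable subjects.** For cohorts 2b–4b the PK footnote to Protocol Table 1.3 ends with "Day 3: pre-dose (Day 2, 24 hour time point), then based on start of inhalation, 30, 60, 120 min, 4 hour". Only four samples follow that dose, so a Cmax at 60 minutes or later leaves at most two points after it, against the three that Appendix B requires. If about two-thirds of subjects are evaluable (assumed: NHV 3/3/3/8, CF Day 1 3/3/6/12, CF Day 1_3 3/3/6), the one-CI rate at slope 1.2 and CV 50% rises from 43/25/71% to 55/38/77%.

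**The case against.** The best defence is that little depends on the sentence. The analysis is descriptive, the SAP disclaims formal testing, and the wording is indicated rather than demonstrated. The slope and its CI are reported, so a wide interval will be seen. Escalation rests on safety and available pharmacodynamic data (Protocol 7.3). All of this stands and limits the consequence, but a prespecified verdict is what a study report will repeat, and this one has no inconclusive outcome.

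A second objection is that one slope across three dose ranges compares departures of unequal size. That is fair. At a common 1.6-fold departure, the one-CI rate for CF Day 1_3 falls to 16/50/70/76%. At a 2-fold departure and CV 50%, one CI contains 1 in only 15% (NHV), 8% (CF Day 1) and 22% (CF Day 1_3) of trials, so the rule usually catches it. At CV 100% those figures are 55, 46 and 60%, so the protection depends on a variability nobody has stated.

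Third, requiring several intervals makes the rule stricter than one CI. That is true, and the two-CI rates are the closer reading. But the stricter rule also fails a truly proportional drug more often, and it still grows more permissive with noise.

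Fourth, the late-sample point rests on a footnote, because the PK row of Table 1.3 is blank in the text available here, and 9.7.4 allows a substitute AUC. The loss of data may therefore be smaller than assumed.

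**Conclusion.** The concern holds. The decision sentence in SAP 9.7.4 is the wrong rule for its purpose; the regression and the reporting of the slope with its 90% CI are sound. The direction of the error needs no assumption about CV, correlation or evaluability. Its size does: across the assumed CVs of 30–100% at a true slope of 1.2, the two-CI pass rate runs from under 1% (CF Day 1, CV 30%) to 77% (CF Day 1_3, CV 100%). The CF Day 1_3 figures also depend on leaving cohort 6 out. The matter is confined to how a secondary PK result is worded, but it should be corrected, because following the plan exactly can yield a claim that the data do not support.

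**What to change.** Delete the sentence that makes proportionality depend on the intervals containing 1, and put in its place text such as:

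> For each population and day, the slope β and its 90% CI will be reported with the implied fold-departure r^(β−1) and its 90% CI, where r is the ratio of the highest to the lowest RDD dosed in that analysis. A CI containing 1 will not be taken as showing proportionality.

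This also removes the question of whether two or four intervals are meant. If the sponsor wants a yes/no rule, the whole interval would have to lie within a prespecified margin, which is for the sponsor to justify.

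The cost is one change of SAP text and one derived column from the same regression output, with no new data. The fold-departure re-expresses the slope interval, so it adds readability rather than information. The report loses a yes/no label and gives an estimate with its uncertainty instead.
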